3.2.3 Eye Bank Procedures for Study Images

Detailed procedures for study images will be provided in the DEKS-Cornea Image Analysis Center (CIARC) Eye Bank Imaging Manual. In screening images for eye bank prepared DMEK tissue, a minimum of central ECD of ≥ 2300 cells/mm² determined by the eye bank at screening will be required along with fulfilling all medical director determined criteria for quality post prep, including assessment of cell damage within the anticipated donor diameter.

3.2.4 DMEK Lenticule Preparation

Detailed procedures are found in the DEKS Eye Bank Procedures Manual. Each DEKS eye bank will perform their DMEK lenticule preparation following their usual technique while documenting technique, and observations as to any problems during the stripping. Most importantly, each eye bank will ensure that the technician performing the prep will be masked as to the diabetes status of the donor.

For both the eye bank- and surgeon- prepared DMEK preps, the extent of endothelial cell damage post prep utilizing trypan blue will be assessed by the masked technician (or surgeon). The masked technician (or surgeon) will also perform an assessment of scroll tightness modified from earlier description whenever possible⁴⁸. Whether eye-bank or surgeon-prepared, the preferred time from DMEK donor preparation to surgery will be at the discretion of the surgeon, but tracked. Also, if corneal tissue is pre-loaded by the eye bank, the eye bank will follow its normal loading procedure according to their standard operating procedures. The loading system will be recorded (i.e., injector, storage container) and the preferred time from loading to surgery will be at the discretion of the surgeon and tracked.

3.3 Laboratory Testing

1. HbA1c

- De-identified whole blood samples will be sent to the central laboratory (ADRL at the University of Minnesota) for sample analysis.⁵³
- De-identified skin biopsy samples for AGE testing will be sent to [name] laboratory at CWRU for sample analysis.

Chapter 4: Transplantation and Follow-up Procedures at Clinical Sites

4.1 DMEK Procedure

DMEK will be performed according to the investigator's usual routine. Aspects of the surgical technique and procedure will be tracked, but not standardized. Data to be collected will include but are not limited to incision size, insertion method, air or gas usage, other procedures (e.g. cataract surgery), and operative complications (e.g., difficult donor preparation, difficult placement).

The surgeon will be masked to donor parameters (e.g. donor age, donor ECD), except the FDA-approved hypothermic (2-8°C) storage solution being employed.

4.2 Post-Operative Management

Postoperative management will be at the discretion of the surgeon based on his/her usual practices. Key aspects of pharmacologic management (e.g. topical corticosteroid usage, glaucoma medications) will be collected on the data forms.

4.3 Study Visits

Protocol-specified post-operative follow-up visits (and visit windows) for the first eye, established to conform to the usual practice and timed from surgery date, will be scheduled as outlined in Section 4.3.1 below.

4.3.1 Study Visits and Windows

Protocol-specified post-operative follow-up visits (and visit windows) for the first eye, established to conform to the usual practice and timed from surgery date, will be scheduled as outlined as below.

Table 2. Study Visits and Windows

VISIT (TARGET DAY)	ALLOWABLE WINDOW (AROUND TARGET DAY/WEEK)
1 Month (Day 30)	+/- 10 days <small>*note an out of window but not missed visit will be allowed up to 100 days and baseline HbA1c assessment is allowable within this time period as well</small>
12 Months (Day 364)	-30 / +100 days

Additional contacts or visits may occur as needed. Additional visits are expected to be performed per standard of care at the discretion of the investigator. A data form will be completed for each protocol visit (1 month and 12 months) capturing data from that visit plus selected data from the medical record from prior standard of care visits. If graft failure is determined and/or a regraft is required on a non-protocol visit, a graft failure form should be completed if and when this occurs.

4.3.2 Procedures at Study Follow-up Visits

The following data will be collected and procedures will be performed at each protocol-specified post-operative follow-up visit, unless otherwise specified:

- Medication history
- Slit lamp examination:
 - ◆ Recipient corneal stroma clarity
 - ◆ Evidence of graft rejection
 - ◆ Donor positioning (*1 month*)
 - ◆ Graft attachment (*1 month*)
 - ◆ Other abnormalities of interest
- Graft failure assessment
- Intraocular pressure
- Pachymetry
- Endothelial imaging
- HbA1c sample collection (*may be performed up to 1 month visit after surgery for baseline measurement and then at 1 year*)
- Record additional procedures after initial DMEK surgery
- Grading of diabetic retinopathy (*1 year*)
- Post-operative complications and other untoward events

4.4 Early Termination Visit

Participants will be asked to come for an end of study visit in the event of withdrawal or early termination for another reason. If graft failure occurs in the absence of re-graft, follow-up is not terminated prematurely. However, if the graft is replaced, follow-up will be discontinued.

Chapter 5: Clinical Procedures

5.1 Corneal Assessment and Slit Lamp Examination

The slit lamp examination should be performed per the investigator's usual routine. Specific details of the data collected from the slit lamp examination are found in the site procedures manual. Any corneal images obtained for standard of care and therefore part of the medical record may be considered study data.

5.1.1 Recipient Corneal Stroma Clarity

The recipient corneal stroma clarity will be assessed by slit lamp examination using the following validated 3-level classification⁵

- clear central recipient stroma
- equivocally cloudy central recipient stroma
- clouded central recipient stroma.

Specific details regarding the grading of recipient corneal stroma clarity for DMEK are found in the Site Procedures Manual. Investigators will be provided a high resolution color standard scale and will be trained and certified on this classification scheme prior to enrolling participants.

5.1.2 Graft Rejection Assessment

Graft rejection will be assessed during the slit lamp examination using a modification of the Collaborative Corneal Transplantation Studies (CCTS) classification and as used in the CPTS.^{5,49} Graft rejection will be classified as definite, probable/ possible, or not present. Details of the assessment of graft rejection are found in the Site Procedures Manual.

The management of suspected graft rejection episodes will be according to the investigator's clinical discretion.

5.1.3 Graft Attachment Assessment

Graft attachment and position will be assessed by the investigator's routine. If the donor button is detached, the percentage of detachment will be documented. The investigator's management of the detachment and/or repositioning will be standard of care and tracked for study purposes.

5.2 Graft Failure Assessment

Graft failure will be assessed and defined as the occurrence of one of the following:

- Cornea which requires regrafting for any reason
- Cornea which remains cloudy without clearing, according to the following:
 - (1) cloudy cornea which does not clear in the first postoperative week and stays cloudy through 8 weeks post-operatively
 - (2) cloudy cornea which was initially clear in the first postoperative week but becomes and remains cloudy for 3 months without clearing.

OR

- ◆ A study participant whose cornea becomes cloudy (clouded recipient central stroma, based on the DEKS grading scale) will be treated by the investigator's usual routine.

For eyes meeting the definition of graft failure above, the principal cause of graft failure will be classified as one of the following:

- Early failure (cloudy cornea in the first postoperative week which does not clear or requires a regraft within 8 weeks), associated with surgical complications
- Primary donor failure (cloudy cornea in the first postoperative week which does not clear or requires a regraft within 8 weeks), in the absence of surgical complications
- Graft rejection (defined as a clouded recipient central stroma following an allograft reaction);
- Non-rejection graft failure (defined as a graft that initially had a clear central recipient stroma and becomes cloudy due to causes other than an immune event. These include: surface failure, infection, glaucoma/hypotony, endothelial decompensation, interface irregularity or opacity, pre-existing stromal scarring, blunt or penetrating trauma, and other causes);
- Refractive/visual graft failure (defined as a graft that requires regrafting due to inadequate vision while the recipient central stroma remains clear).

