Sample Size	Up to 1420 completed surgeries (~947 donors without diabetes and ~473 donors with diabetes) with a goal of 1278 completing the 1-year follow-up
Treatment Groups	Study eyes will be assigned to receive either a cornea from a donor without diabetes or a cornea from a donor with diabetes. Assignment selection will use a minimization procedure which will prioritize assignments in a 2:1 distribution of tissue from donors without known diabetes to tissue from donors with known diabetes as determined by the eye bank. Participants with 2 study eyes cannot receive a cornea from a donor with known diabetes in both eyes. The minimization procedure will attempt to achieve balance on several factors, including the surgeon and whether the recipient had diabetes versus not.
Participant Duration	12 months follow-up after DMEK

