6.2.2.2 Other Adverse Events

All deaths will be reported, with cause of death if known; other systemic events will not be reported unless determined to be related to study participation.

The following events will be reported on a separate online AE form:

[figure not shown]
- non-serious events related to study procedure of blood sample collection that requires some form of medical intervention (*note: expected events such as pain, bruising, irritation at site of fingerstick do not require reporting*)
- non-serious events related to study procedure of specular microscopy that requires medical intervention

The following ocular adverse events of interest, even if serious, will be reported on electronic study visit case report forms and not on separate AE Forms:

- Surgical complications
- Dislocated donor
- Donor detachment
- Clouded recipient corneal stroma
- Wound leak
- Donor wrinkles/folds/curls
- Anterior chamber abnormalities
- New onset glaucoma
- Graft rejection
- Other serious ocular abnormalities (ex. trauma, retinal detachment, suprachoroidal hemorrhage)

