8.4 Outcome Measures

8.4.1 Primary Efficacy Endpoint

- Graft failure within 1 year of surgery as defined in the SAP

Graft failure will be assessed and defined as the occurrence of one of the following:

- Cornea which requires regrafting for any reason
- Recipient cornea remains cloudy after surgery without clearing for 8 weeks or longer

For eyes meeting the definition of graft failure above, the principal cause of graft failure will be classified and described in the SAP. Further, the date of graft failure will also be described in the SAP.

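### An eye clouded but unconfirmed at the 12-month visit has no rule for confirmation or dating, so the visit date can decide its primary outcome

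*Combined protocol and SAP*

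**What the plan says.** Section 5.2 gives two main routes to graft failure. One is "Cornea which requires regrafting for any reason", which needs no waiting period. The other is persistent cloudiness, and for a graft that was clear in the first week this means a "cloudy cornea which was initially clear in the first postoperative week but becomes and remains cloudy for 3 months without clearing". Section 8.4.1, which defines the primary endpoint, words the cloudiness route differently: "Recipient cornea remains cloudy after surgery without clearing for 8 weeks or longer".

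The Protocol Summary sets participant duration at "12 months follow-up after DMEK". Table 2 in section 4.3.1 targets the last visit at Day 364 with a window of -30/+100 days, so Day 334 to Day 464. Footnote 2 to Table 1 limits late recording to the interval between the 1-month and 12-month visits.

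Three passages bear on later ascertainment:
- Section 4.3.1: "If graft failure is determined and/or a regraft is required on a non-protocol visit, a graft failure form should be completed" when this occurs.
- Section 4.4: "If graft failure occurs in the absence of re-graft, follow-up is not terminated prematurely".
- Section 6.2.7 continues data collection past study completion, but only for events that need an AE form. Section 6.2.2.2 lists clouded recipient stroma among the events that "will be reported on electronic study visit case report forms and not on separate AE Forms".

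Section 8.4.1 leaves the date of graft failure to the SAP; the document reviewed contains no dating rule. Section 8.6 plans Kaplan-Meier estimates and a proportional hazards model without imputation.

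**The concern.** The cloudiness route can be met only after a persistence period, but planned observation of an eye stops at a visit whose date varies by up to 130 days. An eye that clouds shortly before that visit, and is not judged to need a regraft, has not met the definition when it leaves. Nothing tells the site to look again.

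The rule then treats identical courses differently. Suppose two grafts cloud on Day 300 and neither is judged to require regrafting. Under 5.2, the eye seen on Day 364 has been cloudy for 64 days and leaves event-free, while the eye seen on Day 400 has been cloudy for 100 days and is a failure. Both visits are within window. Under the 8-week rule the same split occurs for an onset on Day 320: 44 days at a Day 364 visit, 80 days at a Day 400 visit. Reconciling the two definitions therefore changes the size of the gap but does not remove it.

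At stake is the completeness of the sole primary endpoint, and its independence from visit scheduling.

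**Working it through.** **Inputs.** Persistence period: 3 months, taken as 91 days (5.2), or 8 weeks, 56 days (8.4.1, read here as applying also to grafts that clear and later cloud). Last visit: Day 334, 364 or 464 (4.3.1). Planning rates: 4% and 9%, with about 947 and 473 eyes (8.3).

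**Last onset that can be confirmed = visit day minus persistence period.**

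| Last visit | 3 months: last onset | Gap to Day 364 | 8 weeks: last onset | Gap to Day 364 |
|---|---|---|---|---|
| Day 334 | 334 - 91 = 243 | 121 days (33%) | 334 - 56 = 278 | 86 days (24%) |
| Day 364 | 364 - 91 = 273 | 91 days (25%) | 364 - 56 = 308 | 56 days (15%) |
| Day 464 | 464 - 91 = 373 | none | 464 - 56 = 408 | none |

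The gap closes at Day 364 + 91 = 455, or 364 + 56 = 420. In the Day 334 row, 30 of the gap days fall after the visit itself and are ordinary censoring.

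**Events affected.** Expected failures: 947 x 0.04 + 473 x 0.09 = 37.9 + 42.6 = 80.5. The documents give no onset distribution, so the following are assumptions: 30-60% of failures start after week 8, onsets are spread evenly from Day 56 to Day 364 (308 days), all visits fall on Day 364, and the regraft route catches half.
- 3 months: 91/308 = 0.295. Then 80.5 x 0.30 x 0.295 = 7.1 and 80.5 x 0.60 x 0.295 = 14.3; halved, 3.6 to 7.1 events (4-9% of failures).
- 8 weeks: 56/308 = 0.182. Then 4.4 and 8.8; halved, 2.2 to 4.4 events (3-5%).

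**Power.** A pooled-variance test of two proportions (two-sided 5%, 90% power, 2:1) reproduces the table in 8.3: 371 + 742 = 1113 eyes for 9% vs 4%, and 426 + 852 = 1278 for 10% vs 5%. The planned 1278 is thus the table's 5% column, not the 4% stated, which leaves some reserve at the stated rates. With 1278 eyes, and assuming the same share of failures is missed in both groups:

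| Share missed | 9% vs 4% | 10% vs 5% |
|---|---|---|
| 0 | 93.3% | 90.1% |
| 5% | 92.1% | 88.5% |
| 10% | 90.7% | 86.8% |

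**Classification.** Section 8.10 divides eyes into graft failure, incomplete follow-up without failure, and complete follow-up without failure. A clouded, unconfirmed eye that attends its 12-month visit fits only the third group.

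**The case against.** The strongest reply is that the plan already offers several ways to catch these eyes.

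First, the regraft route asks whether a regraft is required, not whether it has been done. An eye judged at Day 364 to need a regraft is a failure at once. This stands, and it confines the gap to eyes that are clouded, unresolved and not judged to need a regraft.

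Second, the window runs to Day 464, and failure forms may come from non-protocol visits. This also stands, so a reader should not infer that late clouding can never be confirmed. But nothing directs sites to see clouded eyes late or again. If visits were spread evenly over the window (an assumption), the mean gap under 5.2 would be 121 x 121 / (2 x 130), about 56 days, which gives about 2-4 events by the formula above.

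Third, a reader might infer that these eyes are scored as successes. No passage says so. In the planned survival analysis they would most naturally be censored event-free. The failure is still missing from the 1-year count.

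Fourth, a reader might infer a bias toward no difference, because section 1.1 cites greater long-term cell loss with diabetic donors. The graft-failure signal it cites is primary or early failure, which falls outside the gap. Concentration of missed failures in one donor group is conjecture.

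Fifth, the SAP is to set the failure date. A dating rule cannot supply persistence data that were never collected.

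**Conclusion.** The point holds as a gap in ascertainment. Followed as written, the plan lets the date of the last visit decide whether a late-clouding eye that is not judged to need a regraft counts as failed. For a Day 364 visit the unconfirmable period is 91 days under 5.2 or 56 days under 8.4.1. It is longer for earlier visits and absent from Day 455 or Day 420 onward.

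The day counts follow directly from the protocol. The event counts do not: they depend on the assumed late share, even spread, regraft share and visit timing. On those assumptions the loss is a few events, and at 9% vs 4% power stays above the planned 90%. This does not threaten the trial's conclusion, but it is an avoidable inconsistency in the primary endpoint.

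**What to change.** In 4.3.1 and 5.2, state that an eye with clouded central recipient stroma at the 12-month visit that has not yet met the failure definition stays open. The site reports graft status from usual-care visits until the cornea clears, a regraft is required, or the persistence period, once reconciled between 5.2 and 8.4.1, is complete. For onsets up to Day 364 this ends by about Day 455, within the Day 464 already allowed for the last visit.

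In 8.4.1 and the SAP, date failure at the onset of the persistent cloudiness, or at the regraft if earlier. Count it if that date is within 1 year of surgery, whatever the date of the last visit. Dating at completion of 3 months would instead push onsets after Day 273 beyond the year even when confirmed. The rule should also say which date applies to an eye that clouds within the year but is found to require a regraft only later.

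The cost is one extra status form and slightly later data closure for a few eyes, with no new procedure. The change does not capture clouding that begins after an early last visit; that remains ordinary censoring.

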5.3 Intraocular Pressure

Intraocular pressure will be measured using the investigator's usual routine.

5.4 Pachymetry

Corneal thickness will be measured using the investigator's usual routine. If there is a choice, slit scanning topography (i.e. Pentacam) corneal thickness maps are preferred. If no measurement can be obtained (e.g. if the cornea is too thick), this will be noted on the data form.

5.5 Specular Microscopy

At the 1 month and 12 month visits, specular microscopy of the central endothelium will be obtained on all participants that have not experienced graft failure.^{5,50,51} Detailed procedures for obtaining best image quality and image transmission will be provided in the DEKS-CIARC Clinical Site Imaging Manual.

5.6 Grading of Retinopathy

Fundus exams will be performed on all enrolled participants at the initial visit and the 12 month visit to grade the presence or absence of diabetic retinopathy; if present, the degree will be grading according to the DRNet grading scales.⁵² Specifics are found in the Clinical Site Procedures Manual.

5.7 Additional Procedures after initial DMEK Surgery

Data on additional procedures performed on the study eye after the initial DMEK surgery will be collected, including, but not limited to:

- air bubbling/repositioning in the first month
- cataract surgery and placement of intraocular lens (anterior chamber, posterior chamber)
- YAG capsulotomy
- refractive procedure (e.g. limbal relaxing incision, LASIK)
- glaucoma surgery (e.g. trabeculectomy, laser trabeculoplasty, tube shunt, mini shunt, other)

5.8 Laboratory Testing

2. HbA1c

- De-identified capillary whole blood samples obtained around the Baseline and 12-month visits will be sent to the central laboratory (ADRL at the University of Minnesota) for sample analysis.⁵³

Chapter 6: Unanticipated Problems and Adverse Event Reporting

6.1 Unanticipated Problems

Site investigators will promptly report to the CC all unanticipated problems meeting the criteria below and the JCHR IRB must be notified within seven calendar days of recognition. For this protocol, an unanticipated problem is an incident, experience, or outcome that meets all of the following criteria:

- Unexpected (in terms of nature, severity, or frequency) given (a) the research procedures that are described in the protocol related documents, such as the IRB-approved research protocol and informed consent document; and (b) the characteristics of the subject population being studied
- Related or possibly related to participation in the research (possibly related means there is a reasonable possibility that the incident, experience, or outcome may have been caused by the procedures involved in the research)
- Suggests that the research places participants or others at a greater risk of harm than was previously known or recognized (including physical, psychological, economic, or social harm)

The CC also will report to the IRB all unanticipated problems not directly involving a specific site such as unanticipated problems that occur at the CC or at another participating entity such as a laboratory. These instances must be reported to the JCHR IRB within seven calendar days of recognition. The Director of the Human Research Protection Program will report to the appropriate regulatory authorities if the IRB determines that the event indeed meets the criteria of an Unanticipated Problem requiring additional reporting.

6.2 Adverse Events

6.2.1 Definitions

Adverse Event (AE): Any untoward medical occurrence in a study participant, irrespective of the relationship between the adverse event and the device(s) under investigation.

Serious Adverse Event (SAE): Any untoward medical occurrence that:

- Results in death.
- Is life-threatening; (a non-life-threatening event which, had it been more severe, might have become life-threatening, is not necessarily considered a serious adverse event).
- Requires inpatient hospitalization or prolongation of existing hospitalization.
- Results in persistent or significant disability/incapacity or substantial disruption of the ability to conduct normal life functions (sight threatening).
- Is a congenital anomaly or birth defect.
- Is considered a significant medical event by the investigator based on medical judgment (e.g., may jeopardize the participant or may require medical/surgical intervention to prevent one of the outcomes listed above).

